## 6 Analysis populations

*The target population (TP)* – all patients, who fulfill the following criteria:

- treatment-naïve or treatment-experienced adult (age at least 18 years) male or female patients with confirmed CHC with genotype 1 (1a and/or 1b) only, receiving combination therapy with the interferon-free ABBVIE REGIMEN  $\pm$  RBV according to standard of care and in line with the current local label. The prescribed ABBVIE REGIMEN needs to be known;
- if RBV is co-administered with the ABBVIE REGIMEN, it has been prescribed in line with the current local label (with special attention to contraception requirements and contraindication during pregnancy);
- patients with voluntarily signed and dated a patient authorization to use and/or disclosure his/her anonymized health data (or informed consent) prior to inclusion into the study;
- patients must not be participating or intending to participate in a concurrent interventional therapeutic study.

Patients who prematurely discontinue earlier than  $\leq$ study day 55 (for 12 weeks treatment) or  $\leq$ study day 139 (for 24 weeks treatment) will be used in analyses on the population with actual EoT time point without windowing conventions adjustment for EoT.

*The core population (CP)* – all patients of the TP, who have started the treatment combination recommended in the current local label for their disease characteristics. Patients, who fulfill at least one of the following conditions, will be excluded from the CP:

- patients with unknown fibrosis status;
- cirrhotic patients with genotype 1a not receiving ribavirin;
- patients with genotype 1 for whom two direct-acting antiviral agents regimen (2DAA) instead of 3DAA is prescribed;
- patients with EoT  $\leq$ study day 55 (for 12 weeks treatment) or  $\leq$ study day 139 (for 24 weeks treatment).

*The safety population (SP)* – all patients who received at least one dose of the ABBVIE REGIMEN.

 This table is based on the table 4 “Analysis time windows” of clinical study Protocol.

 These time windows are intended for the CP allocation filter only. In case of the TP, all patients will be used for the analysis regardless of actual EoT day relevance to EoT time windows.

 This section is based on the sections 9.7.1 “Analysis population, time windows and handling of missing data” and 9.2.1 “Target population” of clinical study Protocol.

P15-743 (HCV RWE)\_ STATISTICAL ANALYSIS PLAN \_ Final 2.0 \_ 02 Feb 2018

The non-core population (NCP) – patients not receiving the treatment recommended in the local label (patients with EoT ≤study day 55 for 12 weeks treatment and patients with EoT ≤study day 139 for 24 weeks treatment).

The core population with sufficient follow-up data (CPSFU) – all CP patients, who fulfil one of the following criteria:

- evaluable HCV RNA data ≥70 days after the last actual dose of the ABBVIE REGIMEN (i.e. data within the SVR12 time window);
- a HCV RNA value ≥50 IU/mL at the last measurement post-baseline (i.e. no virological response achieved at the last measurement on-treatment or post-treatment);
- HCV RNA <50 IU/mL at the last measurement post-baseline, but no HCV RNA measurement ≥70 days after the last actual dose of the ABBVIE REGIMEN due to reasons related to safety (e.g. dropped out due to AE) or incomplete efficacy information (e.g. virologic failure such as relapse is reported in the eCRF but date and value of the corresponding HCV RNA test is missing).

In this way, only patients who had virological response at their last on-treatment or post-treatment measurement, but had no HCV RNA measurements ≥70 days post-treatment for reasons not related to safety or effectiveness (e.g. lost-to-follow-up or patient not willing to perform an additional HCV RNA test ≥70 days post-treatment) will be excluded from this analysis.

Figure 6.1 illustrates the patients selection for CPSFU.

[figure not shown]

Figure 6.1 – The core population with sufficient follow-up data (CPSFU) allocation

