AEs will be coded using the Medical Dictionary for Regulatory Activities (MedDRA) and will be tabulated by primary MedDRA system organ class (SOC) and preferred term (PT). For treatments, surgical and medical procedures the international non-proprietary name (INN) Drug Terms and Procedures Dictionary will be used.

9.7

Data Analysis

9.7.1

Analysis Population, Time Windows and Handling of Missing Data

The target population (TP) is defined as all patients who fulfill the criteria specified in Section 9.2.1. The core population (CP) is defined as all patients of the TP, who have started the treatment combination recommended in the current local label for their disease characteristics. Patients not receiving the treatment recommended in the local

Confidential Information

No use or disclose outside AbbVie is permitted without prior written authorization from AbbVie

Version 3.0 (22 Apr 2015) – country v 1.0 dated 26.06.2015

Page 32 of 61

label will be summarized in the non-core population (NCP). In addition, the core population with sufficient follow-up data (CPSFU) is defined as all CP patients, who fulfil one of the following criteria:

- (1) evaluable HCV RNA data ≥ 70 days after the last actual dose of the ABBVIE REGIMEN (i.e. data within the SVR12 time window)
- (2) a HCV RNA value ≥ 50 IU/mL at the last measurement post-baseline (i.e. no virological response achieved at the last measurement on-treatment or post-treatment)
- (3) HCV RNA < 50 IU/mL at the last measurement post-baseline, but no HCV RNA measurement ≥ 70 days after the last actual dose of the ABBVIE REGIMEN due to reasons related to safety (e.g. dropped out due to AE) or incomplete efficacy information (e.g. virologic failure such as relapse is reported in the eCRF but date and value of the corresponding HCV RNA test is missing). This means only patients who had virological response at their last on-treatment or post-treatment measurement, but had no HCV RNA measurements ≥ 70 days post-treatment for reasons not related to safety or effectiveness (e.g. lost-to-follow-up or patient not willing to perform an additional HCV RNA test ≥ 70 days post-treatment) will be excluded from this analysis.

The Safety Population (SP) is defined as all patients who received at least one dose of the ABBVIE REGIMEN.

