### **5.2 Windowing conventions**

Due to exploratory nature of the study all interim time-points will be separated into visits in the analysis stage. The most detailed possible situation is:

- on-treatment Week 4 from 15 to 42 study days;
- on-treatment Week 8 from 43 to 70 study days;
- on-treatment Week 12 from 71 to 98 study days;
- on-treatment Week 16 from 99 to 126 study days;
- post-treatment Week 4 from 15 to 56 days post EoT.

Table 5.1 describes assignment of time point windows to the following data for purposes of effectiveness, safety and tolerability analyses.

Table 5.1 – Analysis time windows

| Time point             | Time Window  |                        |
|------------------------|--|------------------------|
|                        | 12 weeks treatment   | 24 weeks treatment     |
| Baseline        | Last value prior to start of study treatment (i.e. $\leq$ study day 1) |                        |
| EoT | Last value between   |                        |
|                        | 56 and 98 study days   | 140 and 182 study days |
| SVR12           | Last value between 57 and 112 days post the study day of last dose     |                        |
| SVR24           | Last value between 141 and 196 days post the study day of last dose    |                        |

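### The SAP drops patients who stopped treatment by day 55 or day 139 from the core population, which is likely to raise its SVR12 rate by an unknown amount

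*SAP*

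**What the plan says.** SAP section 6 defines the CP as target population (TP) patients "who have started the treatment combination recommended in the current local label for their disease characteristics". It continues: "Patients, who fulfill at least one of the following conditions, will be excluded from the CP". The fourth condition is end of treatment (EoT) on or before study day 55 for a 12-week course, or day 139 for a 24-week course. Footnote 2 to SAP Table 5.1 says of the EoT windows: "These time windows are intended for the CP allocation filter only". For 12 weeks that window is "56 and 98 study days"; for 24 weeks it runs from day 140 to day 182.

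The non-core population (NCP) is "patients not receiving the treatment recommended in the local label", explained in a parenthesis as "patients with EoT ≤study day 55 for 12 weeks treatment and patients with EoT ≤study day 139 for 24 weeks treatment". In the TP, by contrast, patients who stop early "will be used in analyses on the population with actual EoT time point without windowing conventions adjustment for EoT".

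The supplied protocol (v3.0), section 9.7.1, defines the CP as TP patients "who have started the treatment combination recommended in the current local label" for their disease, with no duration condition. Section 9.7.3 makes the CP the primary effectiveness set. Section 9.7.1 counts HCV RNA still missing after imputation as virological failure, and section 9.7.3.2 lists premature discontinuation as a category of SVR12 non-response. SAP section 16 claims full consistency with the protocol and names only the dropped patient support program regression.

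**The concern.** The primary objective is effectiveness in routine practice. A population fixed by the treatment started answers that question. A population that also requires about two-thirds or five-sixths of the course to be completed answers a different one.

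The day treatment ends is known only after baseline and is related to outcome. SAP Table 4.1 lists adverse events, virological non-response, rebound or breakthrough, and loss to follow-up among the reasons for a deviating duration. Removing these patients probably removes failures from numerator-eligible and denominator counts alike, so the CP rate would look better than the rate in everyone who started label treatment. The core population with sufficient follow-up is a subset of the CP and inherits the filter. The premature-discontinuation row in the CP effectiveness table could then hold only stops after day 55 or 139.

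The NCP wording adds a contradiction within the SAP: patients who started the label combination are described as not receiving it.

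**Working it through.** **1. Cut-offs.** As shares of the scheduled course: 55/84 = 65% and 139/168 = 83%.

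**2. Where the filter seems to come from.** Protocol Table 4 places the EoT measurement from 28 days before to 14 days after actual EoT. Applied to the scheduled end, this gives 84 − 28 = 56, 84 + 14 = 98, 168 − 28 = 140 and 168 + 14 = 182, exactly the limits in SAP Table 5.1. I infer that a rule for assigning measurements became a rule for removing patients; the SAP gives no rationale.

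**3. Bullet against footnote.** The bullet is one-sided (too early). The windows that footnote 2 calls the CP filter are two-sided. Read literally, a course ending after day 98 or 182 fails the footnote but passes the bullet.

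**4. CP against NCP.** The other three CP exclusions (unknown fibrosis status, genotype 1a cirrhosis without ribavirin, two-agent regimen) are not in the NCP parenthesis. As written, CP and NCP do not divide the TP between them.

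**5. The plan's own figure.** Protocol Table 3 and SAP 4.2 give a Clopper-Pearson interval of 84.2% to 94.2% for 158 patients at 90%. Using x = 0.90 × 158 = 142.2, I get 84.23 to 94.20, width 9.97, which agrees. With whole patients, 142/158 = 89.87% (84.1 to 94.1).

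**6. Effect of the filter.** Let d be the share of starters removed, p the SVR12 rate in all starters and s the rate among those removed. Then

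shift = d(p − s)/(1 − d).

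The documents give no value for d or s; Protocol 7.1 says only that discontinuation in Phase III was low. I assume 158 starters and 142 responders, and vary the number of early stoppers k and responders among them r. Example with k = 4, r = 0: d = 4/158 = 0.0253, so the shift is 0.0253 × 0.8987/0.9747 = 0.0233. Shifts are computed before rounding.

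| k | r | Filtered CP rate | Shift (points) |
|---|---|---|---|
| 1 | 0 | 142/157 = 90.45% | +0.57 |
| 1 | 1 | 141/157 = 89.81% | −0.06 |
| 2 | 0 | 142/156 = 91.03% | +1.15 |
| 2 | 1 | 141/156 = 90.38% | +0.51 |
| 2 | 2 | 140/156 = 89.74% | −0.13 |
| 4 | 0 | 142/154 = 92.21% | +2.33 |
| 4 | 2 | 140/154 = 90.91% | +1.04 |
| 4 | 4 | 138/154 = 89.61% | −0.26 |
| 8 | 0 | 142/150 = 94.67% | +4.79 |
| 8 | 4 | 138/150 = 92.00% | +2.13 |
| 8 | 7 | 135/150 = 90.00% | +0.13 |
| 8 | 8 | 134/150 = 89.33% | −0.54 |

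**7. Sign.** The shift is negative only if s > p. For k up to 8, (k − 1)/k is at most 87.5%, below 89.87%, so every stopper would have to respond.

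**8. Small groups.** In an assumed CP analysis group of 30 with 27 responders (90.0%), removing one non-responding stopper gives 27/29 = 93.1%, or +3.1 points.

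**The case against.** **The governing protocol is unseen.** The SAP follows v4.0, while every protocol comparison here uses v3.0, and v3.0 leaves details of the populations to the SAP. This stands: a departure from the governing protocol cannot be proved. The conflict inside the SAP does not depend on the version.

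**An unfiltered population is analysed alongside.** SAP section 9 names no primary population. TP effectiveness is reported overall and by ribavirin use and duration, TP regressions are planned, Table 1.1 counts the NCP and NCP data are listed. If the TP's own label-conformity criterion is applied strictly, the TP is close to the CP plus early stoppers and patients of unknown fibrosis status. Much of this stands as mitigation, and a reader could add patients back by hand. But the SAP lists off-label regimens as exclusions from the CP within the TP, so it expects the TP to contain some. Rates by genotype, Child-Pugh class and prior treatment are planned for the CP only.

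**A truncated course can be read as not receiving the recommended treatment.** That reading is possible for the NCP sentence alone, but it does not fit a CP defined by what was started.

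**Direction is less sure for 24-week courses.** Some patients removed by day 139 had already had 12 weeks. Protocol 7.1 reports 92% response after 12 weeks in the cirrhosis trial, against 96% after 24. Planned 12-week courses are not early stops, but the caution is fair.

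**The effect may be nil.** The table shells allow for the TP equalling the CP, in which case nobody is removed. With one or two stoppers the shift is small beside an interval about 10 points wide. Both points stand.

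**SAP 7.3 rules out imputation.** This does not block the fix. The SAP's main effectiveness table already places missing SVR12 and premature discontinuation under non-response, out of all CP patients.

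**Conclusion.** The concern holds. The set that the supplied protocol makes primary is conditioned on remaining on treatment, and the NCP wording misdescribes the patients removed. Upward bias in the CP and CP-group SVR12 rates is likely but not certain. It requires early stoppers to respond less often than all starters, which is plausible given the listed reasons for stopping and because a stopper with no SVR12 value cannot be a responder.

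The size cannot be stated from the documents. Under the assumed 142/158 it runs from zero with no stoppers to +4.8 points with eight non-responding stoppers, and to −0.5 if all eight respond. How much it matters depends on the number removed. The correction is warranted in any case, because the filter has no stated reason and no planned table undoes it by CP analysis group.

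**What to change.** 1. In SAP section 6, delete the fourth CP exclusion and the parenthesis in the NCP definition. Amend footnote 2 of Table 5.1 so that the EoT window is not a population filter.
2. Analyse early stoppers in the CP with their actual EoT, as section 6 already does for the TP. Count them as SVR12 responders only if the single last HCV RNA value at least 70 days after the last actual dose is below 50 IU/mL (SAP 3.2.1), and otherwise as non-responders. State that this endpoint rule governs where the SVR12 window of days 57 to 112 in Table 5.1 differs.
3. Present the set with EoT after day 55 or 139 only as a labelled sensitivity analysis, with the number removed and their SVR12.
4. If Protocol v4.0 changed the CP, cite the section and still report CP and CP-group SVR12 with early stoppers included. If it did not, correct the consistency statement in SAP section 16.

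The cost is wording in SAP sections 5.2, 6 and 16, revised flags for the CP, the NCP and the core population with sufficient follow-up, and a rerun of the CP tables. No new data are needed. The reported SVR12 may be slightly lower.

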In accordance with the non-interventional nature of the study all HCV RNA measurements will be performed at the sole discretion of the physician and all HCV RNA measurements have to be entered into the eCRF. All recorded HCV RNA values will be assigned to appropriate time points (baseline, on-treatment visits, EoT visit, post-treatment visits). The time windows for the assignments will be specified in the statistical analysis plan (SAP).

No data will be imputed for any effectiveness or safety analyses except for the analyses of the HCV RNA endpoints. When there is no HCV RNA value in a visit time window post-baseline, but prior to EoT, the closest values before and after the window, regardless of the value chosen for the subsequent and preceding window, will be used for the flanking imputation described below. If a patient has a missing HCV RNA value at a post-baseline visit prior to EoT but has undetectable HCV RNA (with LLoD ≤ 50 IU/mL) or unquantifiable, but detectable HCV RNA levels (with LLoQ ≤ 50 IU/mL) at both the preceding and succeeding measurements, the HCV RNA level will be considered undetectable or unquantifiable, respectively, at this visit for this patient. In addition, if a patient has an unquantifiable HCV RNA level at the preceding measurement and an

Confidential Information

No use or disclose outside AbbVie is permitted without prior written authorization from AbbVie

Version 3.0 (22 Apr 2015) – country v 1.0 dated 26.06.2015

Page 33 of 61

undetectable HCV RNA level at the succeeding measurement, or vice versa, the HCV RNA level will be imputed as unquantifiable at this visit for this patient. For virological response at EoT a corresponding backward imputation approach will be applied. This means if HCV RNA is missing at EoT, then unquantifiable or undetectable will be assumed for EoT, if the succeeding HCV RNA value is undetectable or unquantifiable. For SVR12 the single last available HCV RNA measurement ≥ 70 days post-treatment will be used. Subsequent to this flanking and backward imputation, if the HCV RNA value remains missing at a specific time point, then the patients will be considered as virological failure at this time point (i.e. not undetectable or unquantifiable).

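### The CPSFU criteria exclude every core patient without a post-baseline HCV RNA value, whatever the reason, but the plan's own summary sentence does not; if such patients exist, the supplementary CPSFU SVR12 rate is raised

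*SAP*

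**What the plan says.** SAP section 6 admits a CP patient to the CPSFU on any one of three criteria:

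1. "evaluable HCV RNA data ≥70 days after the last actual dose of the ABBVIE REGIMEN";
2. "a HCV RNA value ≥50 IU/mL at the last measurement post-baseline";
3. "HCV RNA <50 IU/mL at the last measurement post-baseline, but no HCV RNA measurement" at 70 days or later, where the later value is missing for a safety reason or because the efficacy information is incomplete. The example given for the latter is a relapse recorded in the eCRF without the date and value of its test.

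The SAP then states the consequence: "In this way, only patients who had virological response at their last on-treatment or post-treatment measurement", with no later value for reasons unrelated to safety or effectiveness, are excluded. Protocol 9.7.1 has the same three criteria and the same gloss ("This means only patients who had virological response at their last on-treatment or post-treatment measurement").

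The Data Analysis part of the Protocol abstract differs slightly: its second and third criteria refer to the last measurement without limiting it to post-baseline values.

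Four other rules bear on the point:

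- Protocol 9.7.1 says that "all HCV RNA measurements will be performed at the sole discretion of the physician".
- Protocol 9.7.1 counts a time point that is still missing after flanking and backward imputation as virological failure.
- SAP section 6 removes patients whose treatment ended by study day 55 (12-week course) or day 139 (24-week course) from the CP before the CPSFU is formed.
- Protocol 9.7.3 places the primary effectiveness analysis on the CP.

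**The concern.** The summary sentence describes a set that loses only uninformative patients: responders when last seen, lost for reasons unrelated to the drug. The listed criteria define a smaller set. A patient who stopped for an adverse event, died, or had a failure reported without a result, and who has no other post-baseline value, meets none of the three. The third criterion was written to keep such patients, yet it fails exactly when the unrecorded test was the patient's only one.

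With testing at the physician's discretion, a CP patient with no post-baseline value is possible. A programmer following the list excludes that patient, and one following the sentence does not. If the patient counts as a non-responder, this choice moves the CPSFU SVR12 rate, and it is left open.

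**Working it through.** **Logic check.** I set every combination of last post-baseline value, availability of a value at 70 days or later, and reason for its absence against both rules.

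| Last post-baseline value | Value at ≥70 days | Reason for absence | Listed criteria | Summary sentence |
|---|---|---|---|---|
| none | no | safety / incomplete efficacy | out | **not excluded** |
| none | no | unrelated | out | **not excluded** |
| <50 | yes | – | in | in |
| <50 | no | safety / incomplete efficacy | in | in |
| <50 | no | unrelated | out | out |
| ≥50 | yes | – | in | in |
| ≥50 | no | safety / incomplete efficacy | in | in |
| ≥50 | no | unrelated | in | in |

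List and sentence agree wherever a post-baseline value exists and conflict in both states where none exists. Read literally, the abstract's second criterion would also admit a patient whose only value is a viraemic baseline, whom SAP 6 and Protocol 9.7.1 exclude.

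**The plan's own figure.** Protocol 9.5 and SAP 4.2 give 158 evaluable patients and an expected SVR12 of 90%, with a Clopper-Pearson 95% interval of 84.2% to 94.2%. With x = 0.90 × 158 = 142.2 the interval is 84.23% to 94.20%, width 9.97 points, so the figure reproduces. With a whole count of 142 it is 84.08% to 94.10%, width 10.02.

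**Size.** Inputs and assumptions:

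- N = 158 patients if the summary sentence is followed. This borrows the planned sample size.
- x = 142 responders, the whole number nearest to 90%.
- k = number of these patients who have no post-baseline value and count as non-responders. The documents do not give k, so a range is shown.

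The rate is x/N with them kept and x/(N − k) with them dropped.

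| k | Rate with k dropped | Change from 142/158 = 89.9% |
|---|---|---|
| 0 | 142/158 = 89.9% | 0.0 |
| 1 | 142/157 = 90.4% | +0.6 |
| 3 | 142/155 = 91.6% | +1.7 |
| 5 | 142/153 = 92.8% | +2.9 |
| 8 | 142/150 = 94.7% | +4.8 |

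The step is similar at a higher rate: 150/158 = 94.9%, 150/157 = 95.5%, 150/155 = 96.8%. Either way it is about 0.6 points per patient, against a planned precision of about 5 points either side.

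**Direction.** The rise depends on counting these patients as non-responders. Protocol 9.7.1 supports this by treating a persisting missing value as failure. So does the shell of SAP Table 2.1.1.1.1, which lists missing SVR12 among the non-response rows with all CP patients as N. SAP 7.3 says that no data are imputed, but it does not remove missing patients from that denominator.

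**The case against.** The strongest reply is that this is a drafting gap with little or no effect.

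- **The group may be empty.** The CP filter already removes early stoppers, who are the likeliest safety dropouts without any test. What remains is a patient treated to at least day 56 (or day 140) with no value on treatment, at end of treatment or afterwards. Protocol Table 2 lists HCV RNA at every visit and asks premature discontinuers to return for end-of-treatment data. Footnotes in the SAP effectiveness shells state that CP and CPSFU hold the same subjects. This stands as a limit on size. It does not settle the rule: testing is discretionary, Protocol 9.7.1 has no such filter, and the SAP shells also plan separate CPSFU tables (2.1.3.1 to 2.1.3.4) if the sets differ.
- **The sentence is only a gloss, and Figure 6.1 may settle the allocation.** The figure is not reproduced in the text reviewed, so this is possible. The written rules would still conflict, because the sentence says that only one kind of patient is excluded.
- **The primary result is untouched.** This stands in full: the primary analysis uses the CP.
- **The true outcome of these patients is unknown.** This also stands. Protocol 9.9 warns that missing HCV RNA data can understate the real SVR rate. The rise shown above is relative to the set the summary sentence describes, under the plan's own missing-equals-failure rule, and not relative to the true cure rate.

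A reader might infer that the CPSFU rate is biased upward as a matter of fact, that treatment failures are being removed, or that the CPSFU regressions (tables 2.4.X.X) overstate effectiveness. The documents support none of these. The count is not given, the virological outcome of such patients is unobserved, and the regressions report odds ratios for predictors, not a rate.

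**Conclusion.** The listed criteria and their stated consequence contradict each other for CP patients with no post-baseline HCV RNA value, in both the SAP and the Protocol.

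The effect on results is conditional. At least one such patient must remain after the CP filter, and these patients must count as SVR12 non-responders. If both hold, the supplementary CPSFU SVR12 rate rises by about 0.6 points per patient at N = 158 and a rate near 90% to 95%. If there are none, as the shell footnotes would imply, it does not change. The primary CP estimate is unaffected in every case.

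This should be corrected because it is cheap and removes an outcome-relevant choice from programming. It does not threaten the primary conclusion.

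**What to change.** - **Third criterion (SAP 6, Protocol 9.7.1):** extend it to CP patients with no post-baseline HCV RNA value whose data are missing for safety or incomplete-efficacy reasons, and state that they count as SVR12 non-responders.
- **Summary sentence:** say that patients lost for unrelated reasons are excluded whether their last post-baseline value was below 50 IU/mL or they had no post-baseline value. Changing the third criterion alone is not enough: a patient with no value and an unrelated reason would still meet no criterion and still fall outside the group that the sentence excludes.
- **Alignment:** bring the Protocol abstract into line by adding the post-baseline limit, and Figure 6.1 if it differs. The SAP cites Protocol version 4.0 and the protocol supplied is version 3.0, so check the current wording first.
- **Reporting:** give the number of CP patients with no post-baseline value, by reason. Table 1.1 shows only the CP and CPSFU totals, which mix these patients with responders lost for unrelated reasons.

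The cost is a few sentences, one programming condition and possibly a slightly lower CPSFU rate.
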